### **A 2        Financial Disclosure**

Investigators and sub-Investigators will provide the Sponsor with sufficient, accurate financial information as requested to allow the Sponsor to submit complete and accurate financial certification or disclosure statements to the appropriate regulatory authorities. Investigators are responsible for providing information on financial interests during the course of the study and for 1 year after completion of the study.

### **A 3        Informed Consent Process**

- The Investigator or his/her representative will explain the nature of the study to the participant and answer all questions regarding the study.
- Participants must be informed that their participation is voluntary, and they are free to refuse to participate and may withdraw their consent at any time and for any reason during the study. Participants will be required to sign a statement of informed consent that meets the requirements of 21 CFR 50, local regulations, ICH guidelines, Health Insurance Portability and Accountability Act (HIPAA) requirements, where applicable, and the IRB/IEC or study centre.
- The medical record must include a statement that written informed consent was obtained before the participant was enrolled in the study and the date the written consent was obtained. The authorised person obtaining the informed consent must also sign the ICF.
- Participants must be re-consented to the most current version of the ICF(s) during their participation in the study.

A copy of the ICF(s) must be provided to the participant.

A participant who is rescreened is not required to sign another ICF if the rescreening occurs within 28 days from the previous ICF signature date.

The ICF will contain a separate section that addresses and documents the collection and use of any mandatory and/or optional human biological samples. The Investigator or authorised designee will explain to each participant the objectives of the analysis to be done on the samples and any potential future use. Participants will be told that they are free to refuse to participate in any optional samples or the future use and may withdraw their consent at any time and for any reason during the retention period.

### **A 4        Data Protection**

- Participants will be assigned a unique identifier by the Sponsor. Any participant records or datasets that are transferred to the Sponsor will contain the identifier only; participant names or any information which would make the participant identifiable will not be transferred.
- The participant must be informed that his/her personal study-related data will be used by the Sponsor in accordance with local data protection law. The level of disclosure and use of their data must also be explained to the participant in the informed consent.
- The participant must be informed that his/her medical records may be examined by Clinical Quality Assurance auditors or other authorised personnel appointed by the Sponsor, by appropriate IRB/IEC members, and by inspectors from regulatory authorities.

## **A 5        Committees Structure**

The safety of all Fusion Pharmaceuticals clinical studies is closely monitored on an on-going basis by Fusion Pharmaceuticals representatives in consultation with Patient Safety. Issues identified will be addressed; for instance, this could involve amendments to the CSP and letters to Investigators.

## **A 6        Dissemination of Clinical Study Data**

A description of this clinical study will be available on <http://www.clinicaltrials.gov> as will the summary of the main study results when they are available. The clinical study and/or summary of main study results may also be available on other websites according to the regulations of the countries in which the study is conducted.

## **A 7        Data Quality Assurance**

- All participant data relating to the study will be recorded on eCRF unless transmitted to the Sponsor or designee electronically (e.g., laboratory data). The Investigator is responsible for verifying that data entries are accurate and correct by physically or electronically signing the eCRF.
- The Investigator must maintain accurate documentation (source data) that supports the information entered in the eCRF.
- The Investigator must permit study-related monitoring, audits, IRB/IEC review, and regulatory agency inspections and provide direct access to source data documents.
- Monitoring details describing strategy (e.g., risk-based initiatives in operations and quality such as Risk Management and Mitigation Strategies and Analytical Risk-Based Monitoring), methods, responsibilities and requirements, including handling of noncompliance issues and monitoring techniques (central, remote, or on-site monitoring) are provided in the monitoring plan.
- The Sponsor or designee is responsible for the data management of this study including quality checking of the data.
- The Sponsor assumes accountability for actions delegated to other individuals (e.g., Contract Research Organisations).
- Study monitors will perform ongoing source data verification to confirm that data entered into the eCRF by authorised site personnel are accurate, complete, and verifiable from source documents; that the safety and rights of participants are being protected; and that the study is being conducted in accordance with the currently approved CSP and any other study agreements, ICH GCP, and all applicable regulatory requirements.

- Records and documents, including signed ICFs, pertaining to the conduct of this study must be retained by the Investigator for 25 years after study archiving or as required by local regulations. No records may be destroyed during the retention period without the written approval of the Sponsor. No records may be transferred to another location or party without written notification to the Sponsor.

## A 8      Source Documents

- Source documents provide evidence for the existence of the participant and substantiate the integrity of the data collected. Source documents are filed at the Investigator's site.
- Data reported on the eCRF or entered in the eCRF that are transcribed from source documents must be consistent with the source documents or the discrepancies must be explained. The Investigator may need to request previous medical records or transfer records, depending on the study. Also, current medical records must be available.
- All information in original records and certified copies of original records of clinical findings, observations, or other activities in a clinical study necessary for the reconstruction and evaluation of the study are defined as source documents. Source data are contained in source documents (original records or certified copies).

## A 9      Study and Site Start and Closure

The study start date is the date on which the clinical study will be open for recruitment of participants.

The first act of recruitment is the first site open.

The Sponsor designee reserves the right to close the study site or terminate the study at any time for any reason at the sole discretion of the Sponsor. Study sites will be closed upon study completion. A study site is considered closed when all required documents and study supplies have been collected and a study site closure visit has been performed.

The Investigator may initiate study site closure at any time, provided there is reasonable cause and sufficient notice is given in advance of the intended termination.

Reasons for the early closure of a study site by the Sponsor or Investigator may include but are not limited to:

- Failure of the Investigator to comply with the CSP, the requirements of the IRB/IEC or local health authorities, the Sponsor's procedures, or GCP guidelines
- Inadequate recruitment of participants by the Investigator
- Discontinuation of further study intervention development

If the study is prematurely terminated or suspended, the Sponsor shall promptly inform the Investigators, the IECs/IRBs, the regulatory authorities, and any contract research organisation(s) used in the study of the reason for termination or suspension, as specified by the applicable regulatory requirements. The Investigator shall promptly inform the participant and should assure appropriate participant therapy and/or follow-up.

Participants from terminated sites will have the opportunity to be transferred to another site to continue the study.

## **A 10      Publication Policy**

- The results of this study may be published or presented at scientific meetings. If this is foreseen, the Investigator agrees to submit all manuscripts or abstracts to the Sponsor before submission. This allows the Sponsor to protect proprietary information and to provide comments.
- The Sponsor will comply with the requirements for publication of study results. In accordance with standard editorial and ethical practice, the Sponsor will generally support publication of multicentre studies only in their entirety and not as individual site data. In this case, a coordinating Investigator will be designated by mutual agreement.
- Authorship will be determined by mutual agreement and in line with International Committee of Medical Journal Editors authorship requirements.

## Appendix B Adverse Events: Definitions and Procedures for Recording, Evaluating, Follow-up, and Reporting

### B 1 Definition of Adverse Events

An AE is the development of any untoward medical occurrence in a participant or clinical study participant administered a medicinal product and which does not necessarily have a causal relationship with this treatment. An AE can therefore be any unfavourable and unintended sign (e.g., an abnormal laboratory finding), symptom (for example nausea, chest pain), or disease temporally associated with the use of a medicinal product, whether or not considered related to the medicinal product.

The term AE is used to include both serious and non-serious AEs and can include a deterioration of a preexisting medical occurrence. An AE may occur at any time, including run-in or washout periods, even if no Study treatment has been administered.

### B 2 Definitions of Serious Adverse Event

An SAE is an AE occurring during any study phase (i.e., run-in, treatment, washout, follow-up), that fulfils one or more of the following criteria:

- Results in death
- Is immediately life-threatening
- Requires in-participant hospitalisation or prolongation of existing hospitalisation
- Results in persistent or significant disability or incapacity.
- Is a congenital anomaly or birth defect
- Is an important medical event that may jeopardise the participant or may require medical treatment to prevent one of the outcomes listed above.

Adverse Events (AEs) for **malignant tumours** reported during a study should generally be assessed as **Serious** AEs. If no other seriousness criteria apply, the 'Important Medical Event' criterion should be used. In certain situations, however, medical judgement on an individual event basis should be applied to clarify that the malignant tumour event should be assessed and reported as a **non-serious** AE. For example, if the tumour is included as medical history and progression occurs during the study, but the progression does not change treatment and/or prognosis of the malignant tumour, the AE may not fulfil the attributes for being assessed as serious, although reporting of the progression of the malignant tumour as an AE is valid and should occur. Also, some types of malignant tumours, which do not spread remotely after a routine treatment that does not require hospitalisation, may be assessed as non-serious; examples in adults include Stage 1 basal cell carcinoma and Stage 1A1 cervical cancer removed via cone biopsy.

The above instruction applies only when the malignant tumour event in question is a new

malignant tumour (i.e., it is *not* the tumour for which entry into the study is a criterion and that is being treated by the investigational product under study and is not the development of new or progression of existing metastasis to the tumour under study). Malignant tumours that – as part of normal, if rare, progression – undergo transformation (e.g., Richter's transformation of B-cell chronic lymphocytic leukaemia into diffuse large B-cell lymphoma) should not be considered a new malignant tumour.

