Prior to the administration of [Ac]-FPI-2068, all AEs related to [In]-FPI-2107 or FPI-2053 should be resolved to Grade 1 or baseline. A delay of 28 days is acceptable from the time of the last [In]-FPI-2107 ( $\pm$  FPI-2053) administration to the administration of [Ac]-FPI-2068 if an AE related to [In]-FPI-2107 or FPI-2053 requires longer time for resolution. In circumstances (e.g., intercurrent illness, etc.) where a delay of [Ac]-FPI-2068 administration may be necessary, the Sponsor and/or Medical Monitor must be consulted to discuss whether the participant can receive [Ac]-FPI-2068. In this scenario, Sponsor and/or Medical Monitor agreement is required prior to [Ac]-FPI-2068 administration. Laboratory results confirming bone marrow and organ function, within retreatment criteria requirements must be documented within 48 hours prior to each cycle of [Ac]-FPI-2068 administration.

Refer to Sections 8.1.4 through 8.1.7 for the assessment details and timepoints performed, and for the biospecimens and information collected during the Treatment Period.

4. *End of Treatment and 28- or 42-Day (+ 14 days) Safety Follow-Up Period:* Participants who do not receive any [Ac]-FPI-2068 (i.e., those who do not enter the Treatment Period) will have a Day 28 ( $\pm$  3 days) safety visit as their last study visit. Participants who receive treatment with [Ac]-FPI-2068 will have a safety visit on Day 42 (+ 14 days) before entering the Extended Safety Follow-up Period.
5. *Extended Safety Follow-up Period:* Because cumulative radiation exposure may be associated with an increased risk of delayed onset of radiation-induced toxicity, participants will undergo additional safety assessments at 3-month intervals. The Extended Safety Follow-up Period will begin 3 months following the last dose of

[Ac]-FPI-2068, and will continue every 3 months for 2 years, then every 6 months for an additional 3 years up to 5 years, or until the participant withdraws from the study (see Section 7.2). Refer to Section 8.1.8 for the assessment details and timepoints performed, and for the biospecimens and information collected during the Extended Safety Follow-up Period.

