### **8.5 AEs and SAEs**

The Principal Investigator is responsible for ensuring that all staff involved in the study are familiar with the content of this section.

The definitions of an AE or SAE can be found in [Appendix B](#).

AEs will be reported by the participant.

The Investigator and any designees are responsible for detecting, documenting, and recording events that meet the definition of an AE.

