#### **8.5.1 Time Period and Frequency for Collecting AE and SAE Information**

Data on AEs and SAEs will be collected from time of signature of the informed consent form, throughout the Treatment Period and including the 28 or 42-day (+ 14 days) safety follow-up

period. During the extended follow-up period, only data for SAEs will be collected.

SAEs will be recorded from the time of signing of the informed consent form.

If the Investigator becomes aware of an SAE with a suspected causal relationship to the IMP that occurs after the end of the clinical study in a participant treated by him or her, the Investigator shall, without undue delay, report the SAE to the Sponsor.

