### **8.5.11 New Cancers**

The development of a new cancer should be regarded as an SAE. New primary cancers are those that are not the primary reason for the administration of the study intervention and have been identified after the participant's inclusion in this study. They do not include metastases of the original cancer.

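### For low-risk new primary cancers, Section 8.5.11 and Appendix B 2 disagree on seriousness, and Section 8.5.1 and Table 25 disagree on what extended follow-up collects

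*Protocol*

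**What the plan says.** Four places in the protocol bear on this.

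- **Section 8.5.11:** "The development of a new cancer should be regarded as an SAE". The section covers primary cancers other than the one under treatment that are identified after inclusion. Its only stated limit is "They do not include metastases of the original cancer".
- **Appendix B 2:** Section 8.5 directs sites here ("The definitions of an AE or SAE can be found in" Appendix B). The default is that malignant tumours "reported during a study should generally be assessed as" serious. Medical judgement may depart from this: "some types of malignant tumours, which do not spread remotely after a routine treatment that does not require hospitalisation, may be assessed as non-serious". Two instances are named, basal cell carcinoma at Stage 1 and cone-biopsied cervical cancer at Stage 1A1. The following paragraph limits the instruction to new tumours, meaning tumours other than the study cancer and its metastases.
- **Section 8.5.1:** "During the extended follow-up period, only data for SAEs will be collected".
- **Table 25, footnote d:** AE monitoring is scheduled throughout extended follow-up, but only for events judged related. Seriousness is not a condition.

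Section 4.1.4 explains why this follow-up exists: "cumulative radiation exposure may be associated with an increased risk of delayed onset of radiation-induced toxicity". It runs every 3 months for 2 years and then every 6 months for a further 3 years.

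**The concern.** Sections 8.5.11 and B 2 both apply to a low-risk new primary tumour and give different answers. Neither cites the other or says which prevails. Before extended follow-up this affects only the label and the 24-hour reporting duty in Section 8.5.9, because all AEs are collected. In extended follow-up Section 8.5.1 makes the label decide whether the tumour is recorded at all. Table 25 then replaces that criterion with a different one, relatedness. For a first-in-human alpha emitter followed for late radiation effects, the record of new cancers should not depend on which page a site consults, nor on a causality judgement that is hard to make for a single late tumour.

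**Working it through.** The protocol states no figure on this point, so the check sets the rules against each other.

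**Step 1: do 8.5.11 and B 2 cover the same events?** Section 8.5.11 covers new primaries identified after inclusion. The B 2 exemption covers tumours other than the study cancer. They overlap on low-risk new primaries such as a Stage 1 basal cell carcinoma first found during follow-up. There, 8.5.11 says SAE and B 2 permits non-serious.

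**Step 2: what is recorded in extended follow-up?**

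| New cancer | Seriousness label | Under 8.5.1 (SAEs only) | Under Table 25 footnote d (related AEs only) |
|---|---|---|---|
| Spreads remotely or needs admission | SAE under both sections | Recorded | Recorded only if related |
| Low-risk, 8.5.11 followed | SAE | Recorded | Recorded only if related |
| Low-risk, B 2 followed | Non-serious | Not recorded | Recorded only if related |

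The second and third rows differ only in the 8.5.1 column, so the seriousness conflict changes recording only for low-risk tumours and only where 8.5.1 is the rule applied. A low-risk tumour called non-serious and judged unrelated is lost under both rules.

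The last column shows a separate problem. Read literally, footnote d would also omit an unrelated second cancer that is serious, whereas Section 8.5.9 requires every SAE to be reported whatever its causality. The conflict between 8.5.1 and Table 25 is therefore at least as important as the one between 8.5.11 and B 2.

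**Step 3: does any planned summary change?** Section 9.4.3 restricts AE summary tables to treatment-emergent events. That window closes at most 42 + 14 = 56 days after the last dose. Extended follow-up starts 3 months after the last dose, so every event in it falls outside the window and is only listed. A tumour missed there is missing from a listing, and from any long-term safety addendum under Section 4.4, but changes no tabulated rate.

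**The case against.** The best defence is that 8.5.11 states the general rule and B 2, as the designated home of the SAE definition, supplies the case-level judgement. That reading is reasonable, but the protocol does not state it, and 8.5.11 is worded without an exception. It can be said further that the exemption is narrow, that Table 25 would catch a related tumour whatever its seriousness, and that no second-cancer endpoint is planned. All three stand and limit the point. None removes it, because Table 25 and 8.5.1 cannot both be followed and a non-serious, unrelated tumour is lost either way.

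Several stronger readings are tempting and are not supported:

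- **Any radiation-related second cancer might go unrecorded because of B 2.** The default in B 2 is serious, and only low-risk, locally treated tumours can leave it.
- **The medical-history example in B 2 contradicts its own limit to new tumours.** B 2 defines new as not the study tumour, so a different, earlier cancer fits. Progression of such a cancer also lies outside 8.5.11, which concerns cancers identified after inclusion.
- **Exclusion criterion 4 makes these events foreseeable.** It concerns cancers known before entry and does not establish how often new primaries will occur.
- **A lost case can be turned into a bias in a second-cancer incidence.** The documents plan no such rate and give no event frequency.

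**Conclusion.** The inconsistency is real and confined to low-risk new primary cancers. For these, seriousness depends on the section followed, and recording in extended follow-up depends on that label under 8.5.1 or on causality under Table 25. The possible loss is in the completeness of late-safety listings. No numerical size can be given, because the documents contain no expected number of such tumours. The conclusion assumes that a site may act on B 2 as the SAE definition, as Section 8.5 invites, and that nothing elsewhere ranks 8.5.11 above B 2 or 8.5.1 above Table 25; the protocol contains no such ranking. The matter is modest, but worth correcting because it touches the stated purpose of the long follow-up.

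**What to change.** 1. State one seriousness rule for new primary cancers, in the same terms in Section 8.5.11 and Appendix B 2, with a cross-reference each way.
2. Reconcile Section 8.5.1 with Table 25 footnote d so that extended follow-up has a single collection rule, consistent with Section 8.5.9.
3. State that all new primary cancers identified after inclusion are recorded to the end of extended follow-up, regardless of seriousness or relatedness.

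The revision should not keep the non-serious exemption for progression of the study tumour: Section 8.5.7 says such progression is not an AE, and B 2 already excludes it. Nor is there a basis for making recurrence of a medical-history cancer a mandatory SAE, since that goes beyond 8.5.11.

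The cost is a short text edit and a few more event forms, with no effect on design, dosing or sample size.

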### **Life-threatening**

'Life-threatening' means that the participant was at immediate risk of death from the AE as it occurred or it is suspected that use or continued use of the product would result in the participant's death. 'Life-threatening' does not mean that had an AE occurred in a more severe form it might have caused death (e.g., hepatitis that resolved without hepatic failure).

### **Hospitalisation**

Outpatient treatment in an emergency room is not in itself a serious AE, although the reasons for it may be (e.g., bronchospasm, laryngeal oedema). Hospital admissions and/or surgical operations planned before or during a study are not considered AEs if the illness or disease existed before the participant was enrolled in the study, provided that it did not deteriorate in an unexpected way during the study.

